#### **4.2.1.2.1.2 Secondary analysis of the primary endpoint**

As a secondary analysis, pairwise testing will be performed as described in section 4. The same ANCOVA model used for the MCP-Mod procedure will be used on singly and multiply imputed data as specified in section 4.1.1.1 and results including the 80% upper and 90% lower 1-sided confidence intervals as well as 95% CIs and nominal p-values tabulated.

#### **4.2.1.2.1.3 CCI**

CCI

#### **4.2.1.2.1.4 Sensitivity analyses of the primary endpoint**

Sensitivity analyses of the attributable estimand will explore different ‘missing not at random’ imputation approaches other than return-to-baseline such as ‘jump to’ reference as described by Cro S. *et. al.*, 2020. That is, the same imputation process as described in section 4.1.1.1 will be used except that in step 2 instead of using the BOCF approach for MNAR, the data of placebo participants would be used as a reference.

#### **4.2.1.2.2 Key secondary endpoints**

##### **4.2.1.2.2.1 Change in WOMAC pain subscale scores**

The same analysis as applied to the primary endpoint will be applied to the change from baseline to Week12 in WOMAC pain subscale scores.

The same summary outputs including listing will be produced as produced for the primary endpoint detailed in section 4.2.1.2.1.

##### **4.2.1.2.2.2 Change in WOMAC physical function scores**

The same analysis as applied to the primary endpoint, excluding the MCP-MOD analysis, will be applied to the change from baseline to Week12 in WOMAC physical function scores.

The same summary outputs including listing will be produced as produced for the primary endpoint detailed in section [4.2.1.2.1](#).

#### **4.2.1.2.2.3 Change in PGA of OA scores**

The same analysis as applied to the primary endpoint, excluding the MCP-MOD analysis, will be applied to the change from baseline to Week12 in PGA of OA scores.

The same summary outputs including listing will be produced as produced for the primary endpoint detailed in section [4.2.1.2.1](#).

### **4.2.2 Other secondary efficacy endpoints**

For each endpoint reported under the other secondary efficacy variables detailed in section [3.3](#), a separate summary table for observed cases only will be produced, as described in section [4.1](#). That is, for other continuous secondary endpoints, the outputs will present the summary statistics for baseline and the change from baseline to corresponding Weeks.

Other continuous secondary endpoints will be analysed by observed cases only. The ANCOVA model with dose, baseline score and KL grade will be used, and results tabulated following the same presentation used for key secondary endpoints except for the asymmetric CI.

For binary secondary endpoints, a logistic regression analysis will be performed with the same covariates as for the respective continuous endpoints. That is, for example the logistic regression for the OMERACT-OARSI endpoint will include baseline WOMAC pain and physical function subscales scores, baseline PGA score and KL grade as covariates in the model. The results will be tabulated so that the number and percent of responders with odds ratios, 95% CIs and nominal p-values will be presented for each week of interest.

Finally, listings will be produced for all other secondary efficacy endpoints.

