## 1.1 Study objectives

### 1.1.1 Primary objective

Primary Objective	Estimand description/endpoint

To assess the efficacy of MEDI7352 compared to placebo on chronic pain in participants with painful OA of the knee at Week 12
	
Population:  Adults with moderate-to-severe chronic OA pain of the knee, persistent for 3 months or longer, not adequately controlled by standard-of-care treatments

	
Primary endpoint:  Change in weekly average of daily NRS pain scores from baseline to Week 12

	
Intercurrent events:
 
 
• Discontinuation due to lack of efficacy or an adverse event (AE)
 
• Discontinuation due to other reasons such as loss to follow-up or external circumstances
 
• Taking prohibited pain medication during the treatment period
 
• Taking excessive permitted rescue medication
 

	
Summary measures:
 
 
• Difference in mean changes in weekly average daily NRS pain scores between MEDI7352 doses and placebo
 
• An ‘attributable’ estimand strategy will be adopted for primary endpoint data missing or affected by any of the above intercurrent events: Missing or affected primary endpoint values will be imputed, but the method of imputation will differ depending upon the intercurrent event. Specifically, data missing due to discontinuation, due to lack of efficacy or an AE will be imputed assuming an unfavourable outcome. Similarly, data affected by prohibited or excessive rescue medication will be set to missing and imputed assuming an unfavourable outcome.
 

AE, adverse event; NRS, numerical rating scale; OA, osteoarthritis.

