### 3 PRIMARY AND SECONDARY VARIABLES

#### 3.1 General principles

##### 3.1.1 Missing data

Unless specifically detailed otherwise, the attributable estimand approach will guide the analysis and summary of primary and key secondary variables, whereas other variables will be analysed and/or summarised using available data only.

For more information on handling of missing data and imputation refer to section 4.1.1.

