**Table 3 Threshold values for the SF-36v2 scale and summary measures**

Threshold	SF-36v2 score									
	PCS	MCS	PF	RP	BP	GH	VT	SF	RE	MH
Group difference	2	3	3	3	3	2	2	3	4	3
Individual change	3.4	4.6	4.3	3.4	6.2	7.2	6.2	6.9	4.5	6.2

BP, bodily pain; GH, general health perceptions; MCS, mental health summary; MH, mental health; PCS, physical component summary; PF, physical functioning; RE, emotional problems; RP, role limitations due to physical health; SF, social functioning; VT vitality.

Categorical analyses of the change in each of the SF-36v2 scales and summary measures will be compared to its respective individual change threshold (see [Table 3](#)) to indicate whether each participant experienced a change deemed clinically significant and important. A participant will be classified as a responder if the change from baseline  $\geq$  individual change threshold, or a non-responder if change from baseline  $<$  individual change threshold. If data are missing, then the participant will be classified as a non-responder.

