## 6 CHANGES OF ANALYSIS FROM PROTOCOL

- The final analysis and its reporting will be split to two deliverables that would be supported by two database locks at timepoints specified in section 1. This is to evaluate the efficacy data once all participants complete the treatment period as it is not anticipated that this data will change rather than waiting once all participants complete the study especially after the follow-up period was extended from 12 to 24 weeks.
- Single imputation will be performed only for the primary and key secondary endpoints as it is not meaningful to perform the single imputation for endpoints that will only be summarised.
- The sequentially rejective multiple comparison approach includes not just pairwise comparisons, but also the dose response curve for the WOMAC pain subscale score. In addition, MCP-MOD analyses of the remaining key secondary endpoints will not be performed.
- Additional supplementary analyses not specified in the protocol were added for comparative purposes within the industry. Those are: ANCOVA analysis of the primary endpoint and WOMAC pain subscale score key secondary endpoint using singly imputed LOCF cases as well as ANCOVA analysis of the WOMAC pain subscale score key secondary endpoint using multiply imputed cases that were imputed using the sampling from normal distribution approach.
- The protocol presents the concomitant medication and therapies as a safety endpoint. However, this data does not necessarily evaluate the safety and hence was moved as part of participant disposition which is in alignment with AZ standard shells reporting.
- CCI [REDACTED].
- The definition of the treatment emergent AEs was clarified to account for instances where a participant withdraws from the study over a phone call and disposition (DS) page in eCRF is populated without the corresponding visit being recorded. In addition, the change in relationship was removed as pre-treatment AE that changes the relationship would need to be entered in the database as a new AE with a start date on or after the first IP administration date and hence would automatically become a treatment emergent AE as per the first part of the definition.
- Other secondary endpoints, DSIS and rescue medication use will be summarised and analysed using available data on protocol specified visits and not just those visits specified in the definition of the endpoint itself (Week 2, 4, 6, 8, 10, 12 and 18).

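### The secondary responder odds ratios are fitted to available data only, dropping participants whom the primary and key secondary analyses of the same scores count as unfavourable

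*SAP*

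**What the plan says.** **Rule for these endpoints.** SAP section 3.1.1 applies the attributable estimand to the primary and key secondary variables, "whereas other variables will be analysed and/or summarised using available data only". Section 4.2.2 then says of each other secondary endpoint that "a separate summary table for observed cases only will be produced". For continuous endpoints it adds: "Other continuous secondary endpoints will be analysed by observed cases only". For responders it says: "For binary secondary endpoints, a logistic regression analysis will be performed with the same covariates as for the respective continuous endpoints". The output is counts and percentages of responders with odds ratios, 95% confidence intervals and nominal p-values at each week.

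**Rule for the same scores higher up.** Section 1.1.1 says that data missing after discontinuation for lack of efficacy or an adverse event, or voided for prohibited or excessive rescue medication, "will be imputed assuming an unfavourable outcome". Table 2 makes this baseline observation carried forward (BOCF), and section 3.3 extends it to the key secondary endpoints.

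**Reason given.** Section 6 confines single imputation to the primary and key secondary endpoints because "it is not meaningful to perform the single imputation for endpoints that will only be summarised".

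**A different rule elsewhere.** For the exploratory SF-36v2 responders, section 3.5.1.3 says: "If data are missing, then the participant will be classified as a non-responder".

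**The concern.** A responder analysis asks what share of those randomised reached a useful improvement. Someone who stops because the treatment did not work or was not tolerated has not reached it, and the plan takes that view for the mean change in NRS, WOMAC and PGA scores. For responder status built from those scores, the same person is left out of the model.

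The odds ratio then compares arms after selection on events that occur after randomisation and may depend on treatment. A responder result could disagree with the primary result on the same scores only because the missing-data rules differ. The reason in section 6 does not cover this, because these endpoints are modelled and not merely summarised.

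**Working it through.** **1. Which rule governs the logistic models?** The explicit observed-cases sentence for analysis names continuous endpoints, and the logistic sentence has no missing-data rule of its own. The rule follows from section 3.1.1 and the opening of section 4.2.2. No other section gives these endpoints a different one.

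**2. Who is dropped?**
- Section 3.2 derives a Week 12 NRS average only for participants who complete treatment. A premature withdrawal has none, and for the primary endpoint it is imputed.
- Section 3.3 reassigns early-termination assessments of all secondary endpoints by study day, in the same way.
- Section 3.2 sets scores to missing when the prohibited or rescue medication criteria are met.
- Section 3.3.1 collects Week 18 WOMAC only from treatment completers. Under section 3.3.2, those who discontinue have their last PGA at early termination.

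Such a participant has no response status at the affected week. Under the single-imputation BOCF of Table 2, change is zero and every improvement threshold is missed.

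**3. Does the section 6 reason hold?** Section 6 says the endpoints are only summarised. Section 4.2.2 plans ANCOVA and logistic regression for them. The two conflict. Section 6 also speaks of single imputation only, so it gives no reason against a non-responder rule or multiple imputation.

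**4. Which denominator?** Section 2.1 makes the full analysis set (all randomised) the set for all efficacy analyses. Section 4.1 bases percentages by default on the whole analysis set in the cohort. The printed percentage may therefore include participants whom the odds ratio beside it excludes.

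**5. Size.** The SAP gives no responder or dropout rates, so there is no figure to reproduce and the inputs below are assumptions. The odds ratios are crude, whereas the planned ones are covariate-adjusted.

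Let p be the observed-case response, m the share missing, and s the share of the missing that is due to an unfavourable event. Other missing values respond at the arm's observed rate. The rate with unfavourable events counted as non-response is p × (1 − m × s).

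*Equal observed response*: p = 0.50 in both arms, unfavourable events in 15% of placebo and 30% of active, no other missing data.
- Observed cases: odds ratio 1.00.
- Placebo: 0.50 × 0.85 = 0.425. Active: 0.50 × 0.70 = 0.350.
- Odds ratio: (0.350/0.650) / (0.425/0.575) = 0.73.
- Events swapped between arms: 1/0.73 = 1.37.

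With the section 4.1 default denominator, this table would print 42.5% and 35.0% beside an odds ratio of 1.00.

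*Unequal observed response*: 40% placebo, 55% active, observed-case odds ratio 1.83.

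| Missing, placebo / active | Half of missing unfavourable | All unfavourable |
|---|---|---|
| 27% / 27% | 1.72 | 1.63 |
| 20% / 35% | 1.48 | 1.18 |
| 35% / 20% | 1.99 | 2.24 |

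For example, in the second row with all unfavourable: 0.40 × 0.80 = 0.320 and 0.55 × 0.65 = 0.3575, so (0.3575/0.6425) / (0.320/0.680) = 1.18.

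**The case against.** The strongest reply is that the scope is deliberate and disclosed. Section 3.1.1 reserves the attributable estimand for the primary and key secondary variables, and a simpler approach for lower-ranked endpoints is a legitimate choice. That would carry weight if section 6 defended it, but the reason given there is contradicted by section 4.2.2. The plan also already uses the stricter rule for a responder endpoint of lower rank.

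Other parts of the reply stand and limit the point:
- A reader might infer that every responder endpoint is affected. The SF-36v2 responders are not.
- A reader might infer that formal tests are at risk. These endpoints lie outside the procedure in section 4.2.1.1 and carry nominal p-values only.
- A reader might infer that the printed response rates are inflated. Under the section 4.1 default they may already count missing participants as non-responders. What the text supports is an unclear denominator.
- A reader might take 255 of 350 in section 1.3 as 27% dropout, so that 50% observed response becomes about 36% (0.50 × 255/350). The 255 is an information equivalent, not a completion rate, and that sum also counts withdrawals for unrelated reasons as non-response.
- A reader might infer bias in favour of active treatment. Table 2 groups adverse events with lack of efficacy and medication use, and the latter could be commoner on placebo.
- The formal imputation in section 4.1.1.1 draws values by regression on baseline data. It is not an exact zero change, so non-response matches the single-imputation version of BOCF more closely than the multiple one.

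**Conclusion.** The point holds for the secondary responder endpoints. Followed as written, their odds ratios exclude participants whose data are missing or voided because of Table 2 unfavourable events, while the primary and key secondary analyses of the same scores impute them as unfavourable. The stated reason for not imputing conflicts with the planned models, and the percentage and the odds ratio may rest on different sets of participants.

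Relative to the unfavourable-outcome strategy, observed cases flatter whichever arm loses more participants to these events. The size cannot be fixed from the SAP. Under the assumed inputs an odds ratio of 1.00 becomes 0.73 or 1.37, and one of 1.83 becomes anything from 1.18 to 2.24. The primary conclusion and type I error control are unaffected. The change should be made because these results will be read beside the primary analysis.

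**What to change.** In section 4.2.2, for each binary secondary endpoint and week:

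1. Classify as a non-responder anyone whose value at that week is missing after discontinuation for an adverse event or lack of efficacy, or is unevaluable under the section 3.2 medication rules applied to that week's own assessment window. Tying the rule to that window avoids penalising medication use in an earlier week when the later score is valid and the primary analysis would use it.
2. For other missing values up to Week 12, derive response from the multiply imputed scores and combine with Rubin's rules.
3. For Week 18, which the section 4.1.1.1 imputation does not reach and where WOMAC comes only from treatment completers, state a simple rule such as missing counted as non-response.
4. Use one denominator for the percentage and the odds ratio, and state it.
5. Keep the observed-case analysis as supportive.
6. Correct the rationale in section 6.

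The cost is SAP wording, modest programming, and response rates somewhat lower than those from observed cases.

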### **4.2.3 Exploratory analysis**

A summary table will be produced for the change in DSIS score from baseline to Weeks 2, 4, 6, 8, 10, 12, and 18 as specified in section [4.1](#) following the same presentation used for summary statistics of primary endpoint.

A summary table will present the change from baseline to Weeks 6, 12, 18 and 32 in the overall health utility score from the EQ-VAS questionnaire, by treatment group. Data will be listed.

The number and percentage of participants above and below the threshold values for the SF-36v2 Scale domains, PCS and MCS will be presented as well as descriptive summary statistics

for scores and change from baseline will be produced by treatment group and visit. Data will be listed.

A separate summary table will be produced for each of the four WPAI:OA endpoints defined in section 3.5.1.4 for the change from baseline to Weeks 12,18 and 32. Data will be listed.

A summary table will be produced for the following HCRU endpoints due to OA at baseline and Weeks 12, 18, and 32: any type of medical service received, use of emergency room and frequency, hospitalisation, and length of stay in hospital, use of any aids or devices, any job loss and length of time. Data will be listed.

A table summarising the incidence and time to discontinuation due to lack of efficacy will be produce.

A summary table with use of rescue medication from baseline to Weeks 2, 4, 6, 8, 10, 12, and 18 will be produced. A separate listing will be produced also.

#### **4.2.3.1 ABPM**

Three ABPM parameters (systolic and diastolic blood pressure and pulse rate) will be evaluated separately for during daytime, night-time and over the 24-hour period as follows:

- Baseline and change from baseline will be summarised descriptively as per section 4.1
- ANCOVA for change from baseline with treatment and baseline ABPM as covariates will be fitted and results including 95% CIs and nominal p-values tabulated.

Absolute mean ABPM values and ABPM mean change from baseline for readings mentioned in section 3.5.3 will be listed for each participant. Abnormal values as defined in section 3.5.3 will be flagged within the listing.

#### **4.2.3.2 Pharmacodynamic analysis**

Only total NgF concentrations will be included and will be listed and summarised by treatment group and timepoint (further subset by ADA status), with the following descriptive statistics presented: n, N<LLOQ, Arithmetic mean and SD, Geometric mean (gSD) and CV% (gCV%), median, minimum and maximum.

Furthermore, the influence of the baseline total NgF on changes in NRS pain scores and any interaction with treatment will be assessed.

In addition, a figure of geometric mean (with and without gSD) total NGF serum concentration over time by treatment group will be generated on a linear and a semilog scales as well as spaghetti plot of individual participant profiles by treatment group (both further subset by ADA status). Available data will be listed.

Total NGF serum concentrations from the initial assay (Q2 assay) will be only listed using the latest raw dataset as provided by Q2. This data will not be mapped to SDTM nor ADaM and hence will not be included in any summary tables or figures nor included in any analyses.

#### **4.2.3.3 Biomarker analysis**

Biomarkers (i.e. soluble biomarkers (e.g., cytokines, chemokines), genomic biomarkers (e.g., RNA, microRNA) and urinary CTX-II concentration (cartilage degradation marker)) and their effects on PK, PD, and efficacy may be investigated. However, any such exploratory analyses will be performed and presented separately from the CSR.

Available biomarker data at time of DBL (e.g., baseline TNF alpha, IL-1 beta, IL-6 and high sensitivity CRP) will however be listed for each participant and summarised using descriptive statistics by cohort. Furthermore, the influence of the baseline biomarkers on changes in NRS pain scores and any interaction with treatment will be assessed.

#### **4.2.4 Pharmacokinetic analysis**

PK concentration data will be listed for each participant and each dosing day and timepoint, and descriptive summary statistics (same descriptive statistics as for total NGF concentrations) will be provided by treatment group and timepoint for all evaluable participants (PK analysis set) and further subset by ADA status.

For the calculation of the descriptive statistics refer to section [3.4.1](#).

In addition, a figure of geometric mean (with and without gSD) serum MEDI7352 concentration over time by treatment group will be generated on a linear and a semilog scales as well as spaghetti plot of individual participant profiles by treatment group (further subset by ADA status). Available data will be listed.

The population PKPD analysis of the study data will be described in a separate modelling analysis plan and will be reported separately from the main CSR.

#### **4.2.5 Immunogenicity analysis**

The number and percentage of participants who display detectable ADA within each ADA response category listed in section [3.4.2](#) will be summarized by treatment group and MEDI7352 Total, based on the safety set for ADA-evaluable participants. Median and range of maximum titer will be provided as appropriate (if a participant has multiple titers, the max post-baseline titer is used for summary statistics calculation).

A table providing ADA category definitions will be produced.

A summary will be provided of the number and percentage of participants who display detectable ADA by visit. Median, Q1, Q3, minimum and maximum of ADA titres by visit will also be included.

Impact of ADA on PK and total NGF concentrations will be explored by presenting serum MEDI7352 concentrations and total NGF concentrations descriptive statistics in ADA-positive and ADA-negative participants.

Summary of TEAEs by ADA categories table will include the number and percentage of participants who had:

- Any AE
- Any AE with an outcome of death
- Any SAE
- Any AE leading to discontinuation of study treatment
- Any AESI
- Any AE leading to withdrawal from study.

TEAEs in ADA positive participants will also be listed.

Immunogenicity results will be listed by participant regardless of ADA-evaluable status. ADA titer will be listed for samples confirmed positive for the presence of ADA.

